Aim 3 is intended to explore future implementation of the redeveloped TLC intervention with respite providers. This provides yet another layer of the tool's feasibility. We will host webinars to demonstrate the features and functionality of the TLC intervention as well as to preview pilot study results from Aim 2, then ask providers for feedback on their likelihood of implementation and barriers to using TLC with their clients.

Together, these three aims represent a comprehensive approach to Stage 1 research activities, with the overall goal of developing an intervention that is scalable to real world applications. Throughout all stages of the proposed project, our team is committed to community-engaged research practices, where community partners will provide input and connect us with potential research participants. Given this pragmatic yet scientifically rigorous approach, the results have the potential to guide and accelerate the eventual implementation of the TLC intervention to community and health care practice.

This application relates specifically to Phase 2 of the project, which specifically addresses Aim 2 where human subjects will be recruited and enrolled.

Study Population

Age of Participants: Over 18 years of age

Sample Size:

At Utah: 150
All Centers: 150

Inclusion Criteria:

Inclusion criteria:

AD/ADRD caregivers who are currently using or interested in using respite, such as home-care respite providers or adult daycare providers, or informally provided by family members or friends.

The caregiver must:

- 1) be the primary caregiver,
- 2) live in the same house with the care recipient,
- 3) have access to and/or interest in using respite at least once a week for a minimum of 4 hours,
- 4) be providing care to a family member with Alzheimer's disease or dementia,
- 5) be English speaking, and
- 6) be age 18 or over.

We will recruit a total of 150 caregivers with purposive selection of caregivers to ensure that we are getting a diverse sample of caregivers (i.e., males and females, racial and ethnic diversity, rural and urban residence, early and late-stage dementia caregivers).

Exclusion Criteria:

- Not a primary caregiver
- Not living in the same house with the care recipient
- No access and/or interest in using respite at least once a week for a minimum of 4 hours
- <18 years of age
- Non-English speaking
- Not providing care to a family member with Alzheimer's disease or dementia

Design

Randomized Trial

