Consenting and enrollment. During Phase 2, which is the only phase of the overall project that has been deemed human subjects research, caregivers will be recruited to participate with the assistance of the community partners (Community Faces of Utah, Utah Coalition of Caregiver Support, and the Utah Telehealth Network) who agreed to collaborate with the investigators. These groups will pass names of potentially eligible caregivers to the research staff. The Project Director and/or RA will then conduct a follow-up call (audio or video) to screen eligibility, describe the project, and obtain verbal consent. Upon receiving verbal consent, Project Director and/or RA will email the participant a full consent document for their records (see documents and attachments).

A home visit and/or teleconference (audio or video) will subsequently be set up to provide an initial orientation for the research participant, as well as to assess the capabilities of their personal technology and internet access. Since this is a pilot test, we would like participants to use their own technology if possible, since it will provide us with information about the usability and feasibility of the intervention as accessed on a number of different types of devices, browsers, and networks. However, if needed, the project will provide a netbook

and/or high-speed internet service to those persons who do not have reliable access to these technologies.

Intervention Description & Random assignment to group #1 or group #2 - The TLC intervention is designed to be a fully self-administered 16-week program, where participants engage with online tools at least once a week. The online TLC intervention will guide participants through goal setting and goal attainment processes to more effectively use their respite time. They will use a digital calendar to schedule, plan, and review the respite time they had each week. Throughout the intervention period, they will receive personalized weekly prompts (via email or text, based on their preferences) giving them instructions and reminders about how to schedule, plan, and review their respite needs. There will be a hotline that caregivers can use to contact a project staff member should they encounter any unanticipated problems or new barriers. The TLC online intervention also includes resource pages to foster success as well as provide information useful to family caregivers

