Participants are also asked to complete daily ecological momentary assessments (EMAs), in which they indicate if they used respite that day, and if so, their experienced and evaluative satisfaction with respite time-use. The daily EMAs will take about 1-2 minutes to complete as they are only 3 items (respite used [yes/no], and two items each measuring experienced and evaluative time-use satisfaction). The caregivers will be prompted weekly to complete their EMAs. Note: as mentioned above, all EMA data collection has been

integrated into the online version of the TLC intervention tools through a digital calendar, combining the TLC intervention with the collection of daily EMA.

Each questionnaire will take about 10-45 minutes to complete. The baseline and final questionnaire are significantly longer than the monthly questionnaires (i.e., 10 minutes versus 45 minutes). Questionnaires will include standardized fixed-choice and open-ended survey questions related to :

- demographic indicators
- caregiving context, and
- caregiver health and well-being (i.e., burden, anxiety, positive affect, global health).

The final questionnaire includes additional measures related to the participants' use of the TLC intervention tools. We will assess their perceptions of feasibility, usability, and acceptability of the online version of the TLC intervention. Other feasibility indicators such as login behavior, intervention protocol completion, and dosage will be imported in real-time directly from google analytics into the secure REDCap data base.

Procedures performed for research purposes only:

[figure not shown]
Statistical Methods, Data Analysis and Interpretation

STATISTICAL DESIGN & POWER

The overall project has three specific aims. This application relates to Aim 2, where which entails human subjects research.

Aim 2: Conduct a hypothesis driven pilot test of the TLC intervention with dementia caregivers

Statistical Design & Power - Aim 2

The purpose of Phase 2 is to conduct a fully-powered pilot study to measure feasibility and efficacy of the TLC intervention with a sample of dementia caregivers (n=120). This section describes the planned analyses to assess efficacy of the TLC intervention.

Study Design

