Time-use satisfaction data will be collected daily using EMA, of short questions. First, did you have respite today? Then, if yes, how satisfied are you with your respite time-use? (1-

5) Did the respite time make you feel more positive/negative about your role as a caregiver? (1-5). These two items measure “experienced” and “evaluative” time-use measures, respectively, which have been theorized to be associated with the wellbeing outcomes (anxiety & caregiver burden). Aggregated averages of these two measures will be computed for specific time-periods (i.e., across the four-week interval spanning the primary data collection timepoints). The same MLM will test significance of time x intervention interaction on mean Time-use satisfaction following TLC intervention compared to WLC.

H3: Higher time-use satisfaction will be associated with lower burden & anxiety (direct effect)

Using the same MLM framework, we will examine if aggregate Time-Use Satisfaction (predictor) is associated with lower “caregiver burden” and “anxiety.” As an exploratory aim we will examine Time (β_1) immediately post intervention through follow up to determine maintenance, attenuation, or no change in Group A outcomes after TLC for wellbeing (anxiety & caregiver burden) and time-use satisfaction (experienced & evaluative time-use).

Figure 3: Time-use mediates TLC impact on Well Being

H4: Higher time-use satisfaction will mediate the effect of the intervention on burden and anxiety (direct & indirect effects)

Figure 3 displays our overall mediation model, whereby TLC intervention improves wellbeing by increasing Respite Time-Use Satisfaction. We hypothesize that “satisfaction with respite time-use” is the factor that links respite use with wellbeing outcomes such that TLC intervention leads to improvements in respite quality that in turn produces better outcomes over time.

Mediation analysis will be conducted as previously outlined for cross-sectional as longitudinal models.^{149, 138, 139} In its simplest form, mediation is represented by three linear equations

$$\text{Mediator (Time-Use)} = i1 + aX + e1 \quad (2)$$

$$Y (\text{Wellbeing}) = i2 + cX + e2 \quad [\text{without mediator}] \quad (3)$$

$$Y (\text{Wellbeing}) = i3 + c'X + bM + e2 \quad [\text{with mediator}] \quad (4)$$

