When substituting the Mediator M in equation 3 the indirect pathway by which the TLC intervention impacts wellbeing through time-use is represented by the product of coefficients $a \cdot b$. If significant, then mediation is present. If the direct pathway c in equation 3 becomes non-significant in equation 4 (c') when conditioning on the indirect pathway, then M is said to fully mediate the relationship between TLC and wellbeing. Importantly, in the models we will control for individual values of the wellbeing outcomes obtained before the start of the TLC intervention. The indirect pathway will be tested using the Sobel test that divides product-of-coefficients $a \cdot b$ by the first-order delta-method standard error of the indirect effect. This value is compared against a standard normal distribution to test for significance.¹⁴⁸ We will also consider additional statistical mediation tests that account for non-normality of the product of coefficients and/or bootstrapping methods for more accurate estimates.¹²¹

Although not stated as distinct hypotheses, we will conduct additional exploratory analyses to further explain for whom and how the intervention achieves its effect. These analyses will be guided by the following questions: Do variations in the receipt of the intervention modify these relationships? For example, do participants that report higher intervention feasibility (i.e., higher satisfaction and usability of the tool) or higher dosage (i.e., they accessed more of the intervention's features) show stronger treatment effects? This will be assessed by replacing the dichotomous intervention variable X (TLC vs. WLC) in equation 1 with measures indicating dosage or perceived feasibility. Similarly, we will explore whether individual characteristics or circumstances modify the relationship between intervention, time-use satisfaction, and wellbeing over time. Here, we will use biologic variables of gender and age as well as measures that capture changes in the context of the caregiving relationship as both control variables and interaction. Finally, we will explore whether treatment effects maintain, attenuate, or no-change once the intervention period ends. This will be assessed using a repeated-measures design using Group A's data from immediately post-intervention through the 8-week follow-up period.

Power and Sample Size

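### H3 and H4 contain no term for the amount of respite, so part of any effect of amount can be credited to satisfaction with respite

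*Combined protocol and SAP*

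**What the plan says.** The section on questionnaires and daily EMAs describes the diary: "they are only 3 items (respite used [yes/no], and two items each measuring experienced and evaluative time-use satisfaction". Under H2 the satisfaction questions depend on the first answer: "Then, if yes, how satisfied are you with your respite time-use". The mediator is then formed from the two ratings: "Aggregated averages of these two measures will be computed for specific time-periods", in four-week intervals matching the questionnaires. The yes/no item decides whether the ratings are asked. No hypothesis or model uses it as a count.

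Under H3, aggregate satisfaction is the predictor of burden and anxiety. Under H4, equation 2 regresses satisfaction (M) on intervention status (X), and equation 4 regresses wellbeing (Y) on X and M. One covariate is named for these models: "in the models we will control for individual values of the wellbeing outcomes obtained before the start of the TLC intervention". The exploratory analyses add tool dosage, perceived feasibility, gender and age, "as well as measures that capture changes in the context of the caregiving relationship as both control variables and interaction". Respite days and hours are not on that list.

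The theory does include respite use. The Measures section ties the mechanism to time-use as well as to satisfaction with it. H4 treats satisfaction as the link between respite use and wellbeing, and states that "TLC intervention leads to improvements in respite quality that in turn produces better outcomes over time".

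**The concern.** TLC could alter how much respite a caregiver takes as well as how well it is spent. The Intervention Description says of participants: "They will use a digital calendar to schedule, plan, and review the respite time they had each week", and the weekly prompts cover scheduling. Amount is not fixed at entry either. A caregiver need only "have access to and/or interest in using respite at least once a week for a minimum of 4 hours", so use can start low and rise.

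Randomisation protects the effect of X on M and the total effect of X on Y. It does not protect the path from M to Y. If caregivers with more respite are both more satisfied and, for other reasons, less burdened, amount is a common cause of M and Y. Adjusting for the pre-intervention outcome does not remove that. The problem arises even when every caregiver has satisfaction ratings, so it is separate from ratings being absent on days without respite.

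H4 is the plan's account of how TLC works, in a Stage 1 study meant to guide later development. Better use of respite and more respite point to different next interventions, and equations 2 to 4 cannot tell them apart.

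**Working it through.** **The plan's own figure.** The plan gives no figure on this point. The nearest is the Power and Sample Size statement of more than 80% Sobel power at n = 75 to 120 for medium paths, with no numerical value for medium. With both paths assumed to be 0.39, simulation gives 67% to 70% at n = 75 and 94% to 95% at n = 120. That concerns power to find a true indirect effect and says nothing about bias from an omitted variable.

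**Inputs from the documents.** n = 120 in two groups of 60; alpha 0.05 (sidedness not stated, two-sided used); the Sobel test; equations 2 and 4 as written.

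**Assumptions, not in the documents.** Coaching raises amount D by d SD (0 to 1.0). D relates to satisfaction with coefficient r1 and to the outcome with coefficient -r2, each 0.3 or 0.5. The true effect of M on Y is zero. The check uses one time point per person, without the pre-intervention outcome or the repeated measures.

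**Bias in b.** Within a group, D has variance 1.
- cov(M, Y) = -r1·r2.
- With M scaled to variance 1, b = -r1·r2: from -0.3 × 0.3 = -0.09 to -0.5 × 0.5 = -0.25.
- With unit error variance instead, var(M) = 1 + r1², so b = -r1·r2/(1 + r1²): from -0.09/1.09 = -0.08 to -0.25/1.25 = -0.20.

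Bias in b does not depend on d. In simulation b is falsely significant in roughly 14% to 79% of trials over both scalings. With d = 0 the range is about the same (15% to 58% with unit errors, 17% to 79% with unit variances). H3 is therefore exposed even if coaching leaves amount unchanged. If r1 = 0 there is no bias.

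**Bias in a*b (unit variances).** a = d·r1, so a*b = -d·r1²·r2, and the total effect is -d·r2. The share wrongly credited to satisfaction is r1², which is 9% at 0.3 and 25% at 0.5. For d = r1 = r2 = 0.5, a*b = -0.0625 out of -0.25.

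**False-positive rate of the Sobel test over the link values (unit variances).**
- d = 0.2: 0.1% to 1.9%
- d = 0.3: 0.1% to 3.3%
- d = 0.5: 0.2% to 9.6%
- d = 0.8: up to 24%
- d = 1.0: up to 39%, reached only with both links 0.5 (19% in the same corner with unit errors)

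A joint-significance test is less conservative: 1.3% to 6.7% at d = 0.2, 1% to 10% at d = 0.3, and 40% to 61% in the 1.0 SD corner. This matters because the plan will also consider bootstrap and non-normal-product tests.

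**With amount in equation 4.** If D is measured without error, b averages about 0, Sobel rejects in at most 1.2% of trials and joint significance in at most 4%. If the day count has reliability 0.5 (assumed), the variance of D left after adjustment is 0.5, and b = -0.5·r1·r2/(1 - 0.5·r1²):
- links 0.3: -0.045/0.955 = -0.047, against -0.09 unadjusted
- links 0.5: -0.125/0.875 = -0.143, against -0.25 unadjusted

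So 52% to 57% of the bias remains.

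**The case against.** The strongest objection is that the treatment contrast may barely touch amount. The Random assignment section gives both groups the tools from day 1, with the same orientation, and says they differ only in virtual coaching. The calendar is therefore not the contrast, and coaching is described mainly as help to spend respite time better. Nothing in the documents supports a rise of 0.5 to 1.0 SD. This stands, and it limits the H4 error. It does not protect H3 or b, whose bias does not need amount to differ between groups.

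Second, the theory may be serial. If amount acts on wellbeing only through satisfaction, nothing is misattributed. That also stands, but it is an assumption the plan could examine and does not.

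Third, a reader might infer that the study records amount only as yes/no. That is true of the EMA. The calendar reviews and the caregiving-context questions might hold more, and the instruments are not reproduced. The omission from the models stands either way, because the plan gives no such data a role.

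Fourth, a reader might infer that a*b will be significant even when satisfaction does nothing. The documents do not support this. Under the named Sobel test, most simulated trials in every setting were non-significant.

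Finally, the Purpose section presents the mechanism hypotheses as exploratory. That argues for a modest change, and the change below is modest.

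**Conclusion.** The point holds in a limited form. H3 and the b path of H4 are open to confounding by amount of respite, and the plan does not use the item that would partly address it. Under the assumed links, b is biased by about -0.08 to -0.25 when its true value is zero. For H4 the more likely harm is a biased a*b rather than a false declaration of mediation: Sobel error is about 2% or less at a 0.2 SD rise in amount and becomes large only for rises the documents give no reason to expect.

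Misattribution is possible, not certain. It requires amount to relate to satisfaction and to affect wellbeing by another route. For H4 it also requires coaching to change amount. All path sizes are assumptions. H1, the total effect on burden and anxiety, is unaffected.

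**What to change.** 1. Derive respite days per four-week interval from the existing yes/no item, together with the number of completed diary days, so that a missing entry is not read as a day without respite.
2. Report both by group beside H2.
3. In H3, add the respite-day count as a covariate.
4. In H4, fit two mediators. Add a separate equation for respite days on X, leave equation 2 as satisfaction on X, and enter respite days beside satisfaction in equation 4. Report each indirect effect. Respite days should not be a predictor in equation 2 of this main model, since that would take the amount-to-satisfaction route out of a.
5. As a sensitivity analysis, fit a serial version (X to days to satisfaction to outcome), since the H4 text places respite use before satisfaction.
6. Use hours in place of days only if the calendar already records them. No new diary field is needed.
7. State that the day count measures amount imperfectly and that other common causes of satisfaction and wellbeing may remain. Word the mechanism conclusion accordingly.

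The cost is SAP wording, one short table, one additional equation and one extra coefficient in each outcome model, with a slightly less precise b where days and satisfaction are correlated. No new data are collected.

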Upon consent, participants will be randomly assigned to Group #1 or Group #2. The study design is akin to a waitlist control design, with group #1 (treatment group) receiving 8 weeks of intervention followed by 8 weeks of continued use of TLC intervention tools, and group #2 (waitlist group) doing respite as usual for 8 weeks, followed by 8 weeks of more intensive coaching from the TLC intervention. Both group #1 and #2 will fill out daily/weekly reviews of their respite use throughout the calendar functions of the TLC intervention tools during the 16-week intervention period, as well as monthly questionnaires at baseline/enrollment, week 4, week 8, week 12, week 16, and week 20.

Note: when we created the online, self-administered version of the TLC intervention, we merged all data collection instruments with intervention prompts into a single online delivery package, so both group #1 and group #2 receive access to the TLC study tools from day 1 and end their access at the end of week 20. This has altered the traditional "waitlist" (i.e., no contact) condition associated with group #2. Both group #1 and group #2 receive the same instructions and orientation to the study on day 1. The groups differ only in the amount and type of "virtual coaching" (instructions and prompts from the TLC website) they receive at week 1 and week 9. Group #1 receives more intensive coaching at week 1, with an encouragement to continue doing it on their own at week 9. Group #2 receives less intensive coaching at week 1, with a more intensive coaching instructions presented to them at week 9.

Self-administered questionnaires and daily ecological momentary assessments (EMAs). Participants in both conditions will complete self-administered questionnaires at baseline, and then every 4 weeks thereafter (for a total of 6 questionnaires, spread across 20 weeks). All questionnaires will be distributed electronically via email. Responses will automatically be recorded in a secure REDCap data base.

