We assume clinically relevant small to medium effect sizes in the main outcomes of interest corresponding to 4-6.5 mean change on the total "caregiver burden" outcome and 1.0-1.4 mean change on the "anxiety" outcome. Power and sensitivity analysis were computed in GPower using RMANOVA finding a total sample of 116 would be sufficient to achieve

power of greater than 90% to detect these effect sizes. Therefore, we will aim to have a final sample size of 120 (60 in each sequence) with a 25% over-recruitment to account for study attrition providing a total sample size of 150.

Sample size and sensitivity analyses for mediation analyses are based on empirical estimates conducted by Fritz and MacKinnon (2007).¹²¹ Assuming medium effects for each of the two parts of the indirect pathways (i.e. TLC->Time-use and Time-use->Wellbeing) in Figure 3, a sample size of 75-120 will provide greater than 80% Power (Sobel148 medium-medium effects) at $p=0.05$.

Missing Data

We will explore missing data patterns in SPSS using the Missing Value Analysis tool. We will specify the pattern fixed effects and interactions utilizing Little's test for Missing Completely at Random. In keeping with an intent-to-treat standard and assuming maximum likelihood estimation, we will use all available data for analyses. It is not necessary to eliminate observations from participants who subsequently drop out, nor is it necessary to impute individual observations. Both practices can bias estimation and distort variability. The maximum likelihood estimates given the observed data points are the values most likely to have generated the complete ensemble of observed sample data under the assumed model. Systematic missingness (as determined by missing data patterns) may be included in our mixed effects model. Potentially non-ignorable missing data will be investigated using multiple imputation sensitivity analyses under a diverse set of covariate predictors. To minimize loss of scale scores due to missing items in a computed scale, we will prorate the respondent's score based on available items. If a respondent is missing more than 30% of the items in a computed score for the primary outcome variables, we will code the scale score as missing.

Note: feasibility is another primary outcome of the pilot test. Feasibility-related analyses are discussed at the end of this document, since the focus on feasibility and the analytic strategies to measure feasibility are shared across Aims 1, 2, and 3.

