Completion of intervention protocol per log-in (assessment, goal-setting, action plan)	$\geq 90\%$
Intervention-related drop-out rate	$\leq 10\%$

Acceptability	Benchmark
Caregiver positive or negative appraisal of intervention	$\geq 90\%$ positive
Caregiver confidence that tool will help make better use of respite time (1=low; 5=high)	Mean ≥ 4
Consider using tool in the future (yes/no)	$\geq 90\%$ yes
Would recommend to other respite users to help them plan their respite time (yes/no)	$\geq 90\%$ yes

Usability	Benchmark
On a scale of 1 to 5, how clear were the instructions on the introductory video?	Mean ≥ 4
On a scale of 1 to 5, how easy was it to complete the time-use assessment?	Mean ≥ 4
On a scale of 1 to 5, how easy was it to go through the goal-setting steps?	Mean ≥ 4
On a scale of 1 to 5, how easy was it to complete an action plan to meet your goal(s)?	Mean ≥ 4
Overall, on a scale of 1 to 5 how easy was the virtual coach to use?	Mean ≥ 4
How easy was the layout on the screen to follow on a scale of 1 to 5?	Mean ≥ 4
To what extent was the information presented clear and concise on a scale of 1 to 5	Mean ≥ 4
To what extent did having a chatline make the tool more useful on a scale of 1 to 5?	Mean ≥ 4
To what extent was the chat line easy to use on a scale of 1 to 5?	Mean ≥ 4
How helpful was the information from the chat line staff on a scale of 1 to 5?	Mean ≥ 4
On a scale of 1-5, how useful were the links to other resources?	Mean ≥ 4

Implementation/Feasibility (from provider perspective)	Benchmark
On a scale of 1 to 5, how likely would you consider using this application as part of your service delivery?	Mean ≥ 4
On a scale of 1 to 5, to what extent do you believe your caregiving clients would be interested in using this virtual time-use coaching tool?	Mean ≥ 4

What features of the virtual coach did you like most? Are there any features of the virtual coach you did not like? On a scale of 1-5, rank each feature of the intervention on its usefulness for your clients?	Mean > 4
In what ways would you incorporate it into how you deliver respite services? What would make you more likely to incorporate this application as part of your service package? What barriers do you believe exist that might make you less likely to incorporate this as part of your service package?	Qualitative examples
What do you think would make your clients more likely to use this tool?	Qualitative examples

Page Break

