Figure 5. RE-AIM Dimensions, Suggested Questions for Evaluating Intervention, and Proposed Study

Dimension	Suggested Questions	Proposed Study
Reach	What percent of potentially eligible participants a) were excluded, b) took part and c) how representative were they?	Tracking and analysis of recruitment and eligibility data
Efficacy or Effectiveness	What impact did the intervention have on a) all participants who began the program; b) on process intermediate, and primary outcomes; and c) on both positive and negative (unintended), outcomes including quality of life?	Hypothesis-driven statistical analyses identifying direct and indirect effects of the intervention's efficacy (Aim 2)
Adoption	What percent of settings and intervention agents within these settings a) were excluded, b) participated and c) how representative were they?	Comparison of provider sample characteristics (Aim 3) to population of respite providers

Implementation	To what extent were the various intervention components delivered as intended, especially when conducted by different (nonresearch) staff members in applied settings?	Qualitative themes describing provider comments about barriers and likelihood of implementation (Aim 3)
Maintenance	
What were the long-term effects (minimum of 6-12 months following intervention)?
 
What was the attrition rate; were drop-outs representative; and how did attrition impact conclusions about effectiveness?
 
To what extent were different intervention components continued or institutionalized? How was the original program modified?
	
Initial maintenance or attenuation of intervention efficacy (after 2 months) will be assessed by exploratory analysis comparing post-intervention wellbeing to follow-up wellbeing (Aim 2)
 
Attrition rates will be calculated and described; missing data will be explored as a potential moderator of intervention efficacy (Aim 2)
 
Stakeholders (Aim 1), caregivers (Aim 2), and providers (Aim 3) will all provide information on how the intervention might be further modified.

Table adapted from: www.re-aim.org

Table 1: Amendments submitted and approved by IRB throughout study

Amendments	Date	Description
Adding RA	9/2/2019	Adding new study personnel
Changing Staff on Project	2/18/2019	Adding new study personnel

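### Acceptability and usability are described only for the week-20 questionnaire, so caregivers who withdraw do not count towards these feasibility indicators

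*Combined protocol and SAP*

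**What the plan says.** The paragraphs on self-administered questionnaires and EMAs (Procedures) list the general questionnaire content as demographics, caregiving context, and health and wellbeing. They then say: "The final questionnaire includes additional measures related to the participants' use of the TLC intervention tools", and continue: "We will assess their perceptions of feasibility, usability, and acceptability of the online version of the TLC intervention". The intervention description sets the schedule as "monthly questionnaires at baseline/enrollment, week 4, week 8, week 12, week 16, and week 20", so the final questionnaire is the one at week 20.

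Figure 4 (Feasibility) sets the benchmarks. Three acceptability items must reach at least 90%: "Caregiver positive or negative appraisal of intervention", willingness to use the tool in future, and willingness to recommend it. The fourth acceptability item (confidence that the tool will help) and all eleven usability items must reach a mean of at least 4 on a 1-to-5 scale. No denominator is given for any of these, and there is no rule for people who left or did not answer. The Missing Data section deals with the efficacy models and scale scores; its closing note names feasibility as a further primary outcome.

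On numbers, the Study Population section states: "We will recruit a total of 150 caregivers". Power and Sample Size gives the derivation: "final sample size of 120 (60 in each sequence) with a 25% over-recruitment to account for study attrition providing a total sample size of 150".

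Figure 4 also benchmarks research-related dropout (at most 10%), intervention-related dropout (at most 10%) and data completion (at least 80%). Figure 5 says attrition will be calculated and described.

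**The concern.** Caregivers who leave because the tool does not suit them are the most informative about acceptability. Followed as written, the plan never puts these questions to them. The indicators therefore describe the views of those who remained to week 20 and completed the last survey, a group likely to be better disposed to the tool than everyone who started.

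At stake is how the feasibility result is read. A statement that at least 90% of caregivers were positive could be taken to cover all who were recruited, when it covers only the survivors. At the plan's own attrition allowance the two can differ noticeably.

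**Working it through.** **Inputs.** Recruited 150 and final sample 120 (Power and Sample Size); acceptability threshold 90%, dropout limits 10% and 10%, completion 80%, usability mean 4 (Figure 4).

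**1. The plan's own figure.** 120 × 1.25 = 150, which reproduces. The implied loss is 150 − 120 = 30, and 30/150 = 20% of those recruited.

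**2. Smallest passing count.** 0.90 × 120 = 108 favourable answers.

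**3. The same result over all 150.** If *f* of the 30 leavers would have been favourable, the share is (108 + *f*)/150.

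| *f* | Share of 150 |
|---|---|
| 0 | 108/150 = 72.0% |
| 4 | 112/150 = 74.7% |
| 15 | 123/150 = 82.0% |
| 27 | 135/150 = 90.0% |
| 30 | 138/150 = 92.0% |

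The reported 90% matches the all-recruited share only if leavers are as favourable as stayers (27 of 30).

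**4. Do the other benchmarks catch this?** 10% of 150 is 15, so 15 research-related plus 15 intervention-related dropouts make 30, with both limits met. If all who remain answer, completion at the last survey is 120/150 = 80%, also met. All three can pass at exactly this loss.

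**5. Smaller loss.** If 15 leave (10%), 135 remain. The minimum pass is 122 (0.90 × 135 = 121.5, rounded up). The range is then 122/150 = 81.3% to (122 + 15)/150 = 91.3%.

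**6. Mean-based items.** Suppose 120 stayers average exactly 4.0 and 30 leavers would have averaged *m*. The overall mean is (120 × 4 + 30*m*)/150: 3.4 for *m* = 1, 3.6 for *m* = 2, 3.8 for *m* = 3. The values of *m* are assumed; the documents give none.

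**7. Counting every non-responder as a failure.** 90% of 150 is 135, more than the 120 expected to remain. Even 120 favourable out of 120 gives 120/150 = 80%. That figure is usable as a bound but not as the benchmark.

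**8. What exit forms could change.** For illustration, if 15 of the 30 leavers return an exit form and none is favourable, the responders' figure falls from 108/120 = 90% to 108/135 = 80%.

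**The case against.** The plan does not ignore leavers. Intervention-related dropout has its own benchmark, attrition is to be described, and log-ins, protocol completion and dosage come from automatic records, not from the final survey. Feasibility is a panel of indicators, and a reader of the whole panel would see the loss. This stands, but seeing the loss does not tell anyone what the leavers thought, and step 4 shows that the panel can pass in full.

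Several stronger readings are tempting, and the documents do not support them.

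- *That fewer than three quarters of starters will have been favourable when the benchmark passes.* This needs at most 4 of the 30 leavers to be favourable. If 15 left because of the tool and were all unfavourable, while the other 15 matched the stayers at 90%, the share would be (108 + 13.5)/150 = 81%. Also, 120 is a sample-size allowance, not a forecast of who will answer.
- *That the 90% threshold covers usability.* It covers three acceptability items only.
- *That the plan's RE-AIM table already requires all starters as the denominator.* The words "all participants who began the program" are in the Efficacy row of Figure 5, as a generic suggested question that the study answers with its efficacy analyses. They set no denominator for acceptability.
- *That a decision to carry TLC forward depends on these percentages.* The benchmarks are described as descriptive, and no go/no-go rule is stated.
- *That the items must be moved because the groups are asked at different distances from coaching.* Week 20 is about 12 and 4 weeks after intensive coaching under the intervention description, or about 8 and 0 weeks under Study Design. But both groups keep access to the tools until the end of week 20, and no between-group comparison of acceptability is planned. The two sections also disagree on when coaching ends.

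Finally, the survey forms are not in the documents. That the items appear only at week 20 rests on the protocol text; the amendment log mentions finalized week-16 and week-20 surveys without their content.

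**Conclusion.** The point holds as a cheap improvement. As described, the caregiver acceptability and usability indicators leave out everyone who withdraws before week 20. For the three 90% items, a bare pass at the planned attrition is compatible with anything from 72% to 92% of the 150 recruited. Both ends are bounds, and the documents do not say where in the range the truth would lie. The mean-based items are subject to the same selection, of a size that cannot be derived from the plan.

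This rests on three assumptions: the final questionnaire is the only one carrying the items; the percentages will be computed among those who answer, which follows from the timing because no denominator is stated; and attrition is at the planned 20%. With less loss the range narrows, as step 5 shows.

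**What to change.** 1. Give the acceptability and usability items in a short electronic exit form at withdrawal.
2. Keep the 90% benchmark on those who answer, exit forms included, and state that denominator in Figure 4.
3. For the three 90% items, report beside it the share of all who began TLC, with non-responders counted as not positive, labelled as a lower bound and not as a replacement benchmark.
4. Define who began TLC before tabulating. The intervention description gives both groups access to the tools from day 1, while Study Design has Group B starting the intervention at week 12. On the second account, a Group B caregiver who leaves before week 12 never began. The two sections must be reconciled.

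The cost is a few minutes for those who withdraw, one extra tabulation, and a possibly less favourable figure. If data collection has closed, items 2 to 4 can still be done without new data, using the final-questionnaire answers alone.
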